Rationale: Initial clinical studies have shown that stimulation of the Dorsal Root Ganglion (DRG) can significantly reduce chronic intractable pain. These results have supported the CE marking of the Spinal Modulation Neurostimulator system in the management of chronic pain. Following the requirements of the AIMDD, Spinal Modulation will also collect clinical data on the commercially available Neurostimulator System.

Objective: The purpose of this Post Market Observational Cohort Study is to evaluate the commercially available Spinal Modulation DRG Neurostimulator system, in the management of chronic post-surgical pain, in patients whom are routinely scheduled to receive a Spinal Modulation Neurostimulator system.

Study design: This is a prospective, single-arm, multi -centre, post market observational cohort study to collect data on pain relief, quality of life, physical functioning, subject safety, and subject satisfaction.

Device: Commercially available Spinal Modulation DRG Neurostimulator System for the management of chronic intractable pain (CE 567069).

Study population: Males and females of at least 18 years of age, suffering from chronic post surgical pain for at least 6 months, whom are routinely scheduled to receive a commercially available Spinal Modulation DRG Neurostimulator System.

Intervention: For the post market observational cohort study, the subjects will be asked to complete the standard evaluation questionnaires at baseline. Under monitored anaesthesia care, subjects will undergo minimally invasive placement of leads in the lateral epidural space of the neural foramen, following standard procedures. Subjects who have a successful trial will be implanted with the internal neurostimulator (INS) and will be followed for 24 months. They will be asked to complete questionnaires at the follow-up visits as per standard follow-up neuromodulation care in the Netherlands.

Follow-up visits: The patients will visit the hospital for the following standard follow-up (FU) visits: Baseline, Trial NeuroStimulator procedure, End of Trial, INS implant, 1 week, 1, 3, 6, 12 and 24 months post-operatively. If necessary, the site may contact the patients telephonically at 8 weeks, 9 months and 18 months FU.

Risks: There are no additional risks or burdens to the patients participating in this post market observational cohort study. The implantation of the system and collection of follow up data is a standard procedure in dedicated neuromodulation Pain Clinics in The Netherlands. The data collected consists of standard questionnaires on pain relief, quality of life, physical functioning, subject safety and subject satisfaction.

1 INTRODUCTION AND RATIONALE

History

Neuromodulation for the treatment of chronic pain has been used for over a century¹. The first use of electricity in the spine for neuromodulation of pain was conducted by Norm Shealy in 1967². The development of spinal cord stimulation (SCS) technology has grown rapidly in the past 40 years and is now used in over 40,000 new patients each year.

Spinal Neuromodulation

Several recent systematic reviews have provided evidence that stimulation technology is a safe and effective treatment option for patients suffering from chronic, intractable pain³⁻⁵. The rate of serious complications is relatively low³⁻⁵. The treatment has been found to be successful in approximately 50% of patients that have a positive stimulation trial period^{6,7}. In the largest prospective trial published to date, Kumar and colleagues found a significant reduction in leg pain when compared to a conventional medical management control group^{6,8}. In a similar manner, Kemler and colleagues found that SCS can be effective in the treatment of complex regional pain syndrome (CRPS)⁹⁻¹¹. Despite varying levels of success in the literature, approximately 50% of patients will not receive adequate pain relief from traditional spinal cord stimulation. This suggests that alternative neuromodulation techniques are needed to improve pain relief in these patients.

Therapy Description

The Spinal Modulation Dorsal Root Ganglion Neuromodulation System consists of a two-phase treatment process: 1) a temporary trial phase and 2) a permanent implant phase. The first phase involves implanting stimulation electrodes (or “leads”) into the epidural space, which are connected to an external Trial NeuroStimulator (TNS) to electrically stimulate the Dorsal Root Ganglion (DRG). If patients experience sufficient pain relief during this trial stimulation, they will receive an Implantable NeuroStimulator (INS) system (phase 2).

Rationale

The use of electrical neuromodulation techniques in the successful treatment of various pain conditions is a proven therapy. Research into the role of the DRG in the development and maintenance of chronic pain has led to the development of an electrical neurostimulator system which specifically targets the DRG. This protocol describes a post market observational cohort study to collect the outcome data of the new commercially available Spinal Modulation DRG Neurostimulator System.

This post market observational cohort study is set up to collect prospective data on the performance of the commercially available Spinal Modulation DRG Neurostimulator system in subjects routinely scheduled to receive this system for the management of chronic post-surgical pain.

2 OBJECTIVES

The objective for this multi-centre post market observational cohort study is to assess the performance of the commercially available Spinal Modulation DRG Neurostimulator System in the management of chronic post-surgical pain. The performance will be measured using the following assessments:

Primary Objective:

- Pain relief measured using a Visual Analogue Scale (VAS).

Secondary Objectives:

- Quality of life (EQ-5D)
- Physical functioning (BPI)
- Pain distribution
- Paraesthesia distribution
- Sleep quality
- Subject satisfaction
- Device safety by monitoring
- Device settings and procedural data

3 STUDY DESIGN

This study is a prospective, single-arm, multi-centre post market observational cohort study, designed to assess the clinical effects of the commercially available Spinal Modulation DRG Neurostimulator System, in the management of chronic post-surgical pain. Subjects that are routinely scheduled to receive DRG stimulation will be asked to participate in this observational cohort study. They will be screened based upon the standard inclusion and exclusion criteria for neuromodulation in The Netherlands. Informed Consent will be obtained and they will then be enrolled into the cohort. Baseline parameters will then be measured in subjects using standard questionnaires and according to standard neuromodulation practice.

The study consists of two distinct phases in which the patients are asked to complete questionnaires, corresponding to the two-phase treatment process: 1) Temporary Trial Stimulation, and, 2) Implantable Stimulation (Figure 1).

Subjects will “trial” an external neurostimulator system for a period of time in line with standard hospital practices but no longer than 30 days (phase 1). If subjects experience sufficient pain relief in their primary area of pain, according to current neuromodulation guidelines, they will be eligible to proceed with the second phase of the treatment. If the

eligible subjects agree to move forward into Phase 2, they will undergo another surgical procedure in which the Spinal Modulation implantable Neurostimulator will be implanted. Subjects will be seen for follow-up at 1 week, 4 weeks, 3 months, 6 months, 12 months and 24 months following implantation (Figure 1). The site can contact the subjects telephonically for a follow-up at 8 weeks, 9 months and 18 months if desired (optional).

[figure not shown]

Figure 1. Basic design and follow-up schedule for subjects enrolled into the post-market observational cohort study. Subjects who have consented and been enrolled will undergo a two-phase process for advancement through the cohort. A detailed follow-up schedule can be found in the *Methods* section.

Protocol Phase 1 – Temporary Trial Neurostimulation

Following consent and entry into the post market observational cohort study, baseline parameters will be measured by means of the standard evaluation questionnaires used in The Netherlands

Protocol Phase 2 – Implantable Stimulation and Follow Up

If subjects experience sufficient pain relief in their primary area of pain during the TNS procedure or during the course of the trial phase, they will be eligible for INS implantation. Subjects will be followed for 24 months following implant, returning to the clinic at regular follow-up intervals (1 week, 4 weeks, 3 months, 6 months, 12 months and 24 months). Subjects have the option to return to the clinic at unscheduled times to have the device reprogrammed as needed or for other reasons. This can be captured as an interim visit. The site may contact the patients by phone at 8 weeks, 9 months and 18 months for follow-up (optional).

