4.4 Sample size calculation

As this is a post market observational cohort study, no sample size calculations are necessary. We aim to enrol 30 subjects in this cohort.

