7.3 Study procedures

During the post market observational cohort study, data will be collected on Case Report Forms (CRFs). A copy of the CRFs will be provided for review.

Subject Screening and baseline

Subjects presenting with chronic post-surgical pain for at least 6 months will be screened for possible entry into the post market observational cohort study. Subjects will be screened according to the Inclusion/Exclusion criteria and only subjects meeting all Inclusion criteria and none of the Exclusion criteria will be enrolled. The post market observational cohort study will be explained to all subjects and subjects will provide informed consent prior to any data collection for the study. Subjects will be allowed to discuss their participation in the cohort with the study physician, clinical staff, family, friends and personal or external physician.

Following subject screening and acquisition of Informed Consent, subjects will undergo a baseline assessment to collect clinical data prior to lead implantation and stimulation.

Trial Stimulation Lead Implant Procedure

Following collection of baseline measurements, subjects will begin Phase 1 of the two-step treatment process.

End of TNS Trial Phase

At the end of the Trial Phase, pain relief will be assessed to determine whether a subject should receive an INS implant. The duration of the trial will be at the investigators discretion and in line with current clinical practice. This may be done in the theatre during the TNS procedure or after an extended trial period but should be no longer than 30 days.

INS Implant Procedure

Eligible subjects willing to continue with the implant will undergo surgery to implant the internal neurostimulator (INS). If the subdural leads are removed during the trial period, new leads will also be implanted at this time (see Physician Implant Manual for detailed information regarding the procedure). Each subject will receive a hand-held Patient Programmer that can be used to adjust stimulation amplitude as needed.

Regular Follow-ups

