Subjects will be followed according to the standard follow-up schedule for 24-months following implant at regular intervals: 1-week (± 5 days), 4 weeks (± 1 week), 3 month (± 2 weeks), 6 month (± 2 weeks), 12 months (± 2 weeks) and 24 months (± 2 weeks). The given time-windows are advisable and therefore visits outside the time windows will not be seen as a protocol deviation. If desired, the Investigators may contact the subjects telephonically for evaluations at 8-weeks, 9-months and 18 months post-implant.

Prior to completing the required measurements, the subject will have his/her stimulator reprogrammed if needed or applicable.

24-month follow-up (Study Exit)

The study will end 24 months following INS implantation. At this visit, the regular follow-up assessments as outlined in appendix A will be acquired and a trial exit form will be completed.

Following completion of the study, subjects will continue to use the Spinal Modulation DRG Neurostimulator System. They will be monitored by their physician in accordance with standard medical procedures.

Interim Programming/Revision/Replacement/Explant (if necessary)

During the course of the cohort, subjects will have the option to return to the study site at any time to have their neurostimulator re-programmed to achieve maximal benefit. If any part of the Spinal Modulation Neurostimulator System becomes dysfunctional or requires adjustment following implantation, the patient will come to the site for analysis of the problem (interim visit). In appendix A, the assessments are listed for an interim visit and a revision (if applicable).

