7.6 Follow-up of subjects withdrawn from treatment

Any patient leaving the study will receive standard follow-up care in accordance with the criteria of the Dutch Neuromodulation Society.

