8.2 Adverse and serious adverse events

Adverse events are defined as any undesirable experience occurring in a subject during the study, whether or not considered to be related to the Spinal Modulation DRG Neurostimulator System. All adverse events reported spontaneously by the subject or observed by the investigator or his staff will be recorded.

Adverse events related to the commercially available Spinal Modulation DRG Neuromodulation System will be reported to Spinal Modulation representatives and handled according to the Spinal Modulation internal vigilance regulations for CE marked products.

Clinical study staff will start assessing subjects for adverse events (AEs) once the Informed Consent form has been signed and at each visit thereafter. They will be instructed to request AE information in a nonspecific, non-suggestive manner. Investigators will report all AEs regardless of causality.

Serious Adverse Events (SAE):

A serious adverse event is any untoward medical occurrence or effect that:

- results in death;
- is life threatening (at the time of the event);
- requires hospitalization or prolongation of existing inpatients' hospitalization;
- results in persistent or significant disability or incapacity;
- is a congenital anomaly or birth defect;
- is a new event in the cohort likely to affect the safety of the other study subjects, such as an unexpected outcome of an adverse reaction, major safety finding from a newly completed animal study, etc.

Important medical events that may not result in death, be life-threatening, or require hospitalization may be considered an SAE when, based upon appropriate medical judgment, they may jeopardize the patient and may require medical or surgical intervention to prevent one of the outcomes listed in this definition.

For the purposes of this study the following events will not be reported as serious adverse events due to the nature of the treatment.

- Prolonged hospitalization as a result of a revision procedure, which is allowed in the protocol.
- Hospitalization as a result of or in conjunction with treatment that is part of the subject's conventional medical management.

All SAEs must be reported within 24 hours of the investigational site's knowledge of the occurrence by entering the required information into the appropriate CRF.

The following SAE information will be provided as available:

- Patient ID;
- SAE term, onset date, severity, and causal relationship;

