8.3 Follow-up of adverse events

All adverse events determined to be device related will be followed until they have abated, or until a stable situation has been reached. All AEs determined to not be device related will be followed through the end of the study. All SAEs, regardless of the relationship to the device will be followed until resolution or stabilization unless the subject is lost to follow-up. Depending on the event, follow up may require additional tests or medical procedures as indicated, and/or referral to the general physician or a medical specialist.

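### After the trial phase, all scheduled visits and the study end run from INS implantation, so late lead-procedure complications in subjects who get leads but no INS are picked up only passively and may be under-counted.

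*Combined protocol and SAP*

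**What the plan says.** **Exposure.** Section 5.1 describes Phase 1 as percutaneous placement of leads in the epidural space. Everyone who enters Phase 1 therefore has the lead procedure, whether or not an INS follows. Sections 3 and 7.3 give two ways of not reaching the INS: insufficient pain relief, or an eligible subject not agreeing to go on.

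**Length of the trial.** Section 7.3 says of the end-of-trial assessment: "This may be done in the theatre during the TNS procedure or after an extended trial period but should be no longer than 30 days".

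**Follow-up.** Section 3, under Phase 2, says: "Subjects will be followed for 24 months following implant, returning to the clinic at regular follow-up intervals". The visits are at 1 week, 4 weeks and 3, 6, 12 and 24 months. The optional telephone contacts at 8 weeks, 9 months and 18 months are also counted from implantation. Section 7.3 adds: "The study will end 24 months following INS implantation".

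**AE collection.** Under section 8.2, staff assess AEs "once the Informed Consent form has been signed and at each visit thereafter". The same section also records AEs that subjects volunteer or that staff observe.

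**AE follow-up.** Section 8.3 follows device-related AEs and all SAEs until they resolve or stabilise. For the rest: "All AEs determined to not be device related will be followed through the end of the study".

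**Leaving the study.** Section 7.6 says: "Any patient leaving the study will receive standard follow-up care in accordance with the criteria of the Dutch Neuromodulation Society".

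Device safety is a secondary objective in section 2.

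**The concern.** Active questioning about AEs is tied to visits, and after the trial phase the visits are tied to implantation. A subject with leads but no INS has had the procedure, yet drops out of active questioning when the trial ends. If the trial is judged in theatre and fails, that is the day of the procedure.

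Section 6.2 lists infection and headache among the common risks, and CSF leakage, hematoma and nerve damage among the very rare ones. It is a reasonable inference, though the protocol does not say so, that some of these can appear after the leads are out.

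What is at stake is even ascertainment for a stated secondary objective. If late complications are sought in one group and only received in the other, a summary of lead-procedure safety will tend to look better than it should. The shortfall would fall on subjects who took the procedural risk without going on to the implant.

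**Working it through.** The plan gives no figure to reproduce. On sample size, section 4.4 says "As this is a post market observational cohort study, no sample size calculations are necessary" and then "We aim to enrol 30 subjects in this cohort". The check is therefore mainly a comparison of the schedule for the two groups.

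| | INS implanted | Leads placed, no INS |
|---|---|---|
| Lead procedure (5.1) | yes | yes |
| End-of-trial assessment (7.3) | yes | yes, 0 to 30 days after lead placement |
| Scheduled clinic visits after the trial (3, 7.3) | 6, over 24 months | 0 |
| Optional telephone contacts (3, 7.3) | 3 | 0 |
| Stated study end (7.3) | 24 months after INS | none |
| Volunteered or observed AEs recorded (8.2) | yes | yes, while the subject counts as in the study |
| Interim visit (3, 7.3) | yes | unclear |

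The last two rows need care.

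- Section 8.2 limits AEs to events arising while the subject is in the study. Without an exit point for non-implanted subjects, it is unclear whether a complication reported some weeks after a failed trial qualifies.
- Section 3 allows unscheduled returns for reasons other than reprogramming, but it does so under the Phase 2 heading. Section 7.3 describes interim visits in terms of reprogramming or a system problem after implantation.

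**Scale, for illustration only.** Two inputs are assumptions, because the documents give neither: the share not implanted (10% to 50%) and the late-complication rate *q* (2% to 10%).

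- Number not implanted: *m* = 30 × 0.10 = 3 to 30 × 0.50 = 15.
- Expected late complications among them: *m* × *q* = 3 × 0.02 = 0.06 to 15 × 0.10 = 1.5.
- Chance of at least one: 1 − (1 − *q*)^*m*.
  - Low end: 1 − 0.98^3 = 0.06.
  - Middle (9 subjects, 5%): 1 − 0.95^9 = 0.37.
  - High end: 1 − 0.90^15 = 0.79.

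These are events that could occur in the group, not events that would be missed. Some would be caught passively, and the documents do not allow that fraction to be estimated. If the rate were reported over all 30 subjects, one missed event would move it by 1/30 = 3.3 percentage points.

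**The case against.** The strongest reply is that capture is passive, not absent. Section 8.2 records volunteered and observed AEs with no restriction to implanted subjects. Section 7.6 keeps those who leave in standard neuromodulation care, where staff could see a complication. This stands. A reader might infer that late complications in this group go uncounted, or that these subjects cannot contribute such events. The documents do not support that.

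A reader might also infer that the reported complication rate would fall in proportion to the share not implanted. That needs every late event in the group to be missed and a denominator that includes the group. Section 9 defines no complication rate, safety population or denominator, so no bias of a stated size can be attributed to the plan.

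Three further points stand in part.

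- Three of the five risks named above are listed in section 6.2 as very rare, so high late-complication rates should not be assumed.
- The undated end of study in section 8.3 governs only AEs judged not device related. Section 8.2 includes deployment and implantation of the device among the device-related categories, so a procedural complication so classified by the end of the trial is followed until it abates or stabilises. That provision follows known events; it does not find new ones.
- Figure 1 is not shown and the Appendix A columns have collapsed, so an exit form at failed trial cannot be ruled out.

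Finally, this is a 30-subject observational cohort built on standard-care visits, and the number of events involved may be well below one. That argues for a light remedy rather than none.

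**Conclusion.** The gap holds as a matter of design. In the readable text, a subject with leads placed but no INS has no scheduled AE assessment after the end of the trial and no stated study exit. Ascertainment of late lead-procedure complications is therefore less complete in this group than in implanted subjects, and such events may be under-counted.

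The size is unknown. The illustrative range of 0.06 to 1.5 events occurring in the group rests entirely on assumed rates, and only an unknown part of those would be missed. The primary VAS objective is not affected by this point. Confidence is moderate, because the figure and table that might show an exit or contact for these subjects cannot be read. The change is worth making because it is cheap and serves a stated secondary objective.

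**What to change.** 1. In section 7.3 and Appendix A, add a telephone AE contact for every subject who had leads placed but receives no INS. Use the 1-week and 4-week intervals already in the protocol, counted from lead removal. Record on CRF-17 and CRF-18, and close with CRF-21.
2. In section 8.3, define the end of the study for these subjects as the last such contact. This also settles whether a late report falls within the AE definition in section 8.2.
3. In section 9, state that lead-procedure AEs will be reported over all subjects who underwent lead placement, broken down by implant status.

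The cost is protocol wording and one or two calls for each non-implanted subject: about 3 to 15 subjects under the assumed range. Existing forms are used, with no extra procedure or staff. Only data collection changes, not clinical management. Under section 11.2, the sponsor would need to judge whether the amendment bears on the WMO applicability decision and so must be notified.
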